7.9 Rationale for Subject Selection

The primary anticipated benefit of ISIS 304801 is TG reduction. The severity of hypertriglyceridemia in patients with lipodystrophy is quite variable. In this study, we are targeting the patient population to those with severe hypertriglyceridemia (>500 mg/dL) who are not only at increased risk for cardiovascular disease, but also at risk for acute pancreatitis. Patients with generalized lipodystrophy already have available a highly effective, approved therapy: leptin replacement. However, there are currently no approved therapies for patients with partial lipodystrophy. Hence, the population of partial lipodystrophy patients with severe hypertriglyceridemia has substantial unmet medical need, and has the greatest benefit to risk ratio from participation in this study. Based on our experience, we expect that the majority of subjects who enroll in this study will be female as females typically present with greater metabolic derangement. In addition, we anticipate that the majority of subjects will be Caucasian based on the demographics of partial lipodystrophy. Patients under 18 years of age are excluded as severe metabolic complications of partial lipodystrophy typically develop in adulthood, and there currently is no safety data for ISIS 304801 in children. Because there is a prospect for direct benefit, non-institutionalized adults who are unable to give informed consent but are considered able to comply with the study demands, will be eligible. If we enroll patients who are unable to provide their own consent, we will follow the procedures specified in NIH SOP 14E (“*Research Involving Adults Who Are or May Be Unable to Consent*”). If the study team has a concern that an adult patient may be unable to consent, the NIH Ability to Consent Assessment Team will be contacted to independently assess the subject’s ability to provide informed consent. If the NIH Ability to Consent Assessment Team (ACAT) determines that the subject is not able to consent, an appropriate surrogate (assessed by the NIH ACAT) will be assigned. Consent for research participation will then be obtained from either the surrogate or a legally authorized representative. Individuals designated as durable power of attorney (DPA) for health care or other valid advanced directive, or court-appointed guardians are accepted as legally authorized representatives. If after study enrollment, the patient is unable to comply with the protocol demands, they will be withdrawn from the protocol.

7. Glucose and Lipid Turnover: The stable isotopes ¹³C is not associated with any toxicity at the doses used in these studies ⁵⁴. Deuterium at the doses given may cause temporary dizziness. This risk will be minimized by dividing the ²H₂O dose into four aliquots, and by giving the doses at night while subjects lie in bed. If subjects need to get out of bed (e.g. to use the bathroom) the patient will first sit upright in bed for a few minutes prior to standing, and a nurse will be available to supervise and assist. Palmitate must be complexed to albumin prior to delivery, and thus carries the risks associated with use of human blood products. To minimize exposure to human albumin, uniformly labeled ¹³C₁₆ palmitate will be used, permitting use of the minimum possible dose of this tracer.
8. Euglycemic Hyperinsulinemic Clamp Study: In order to assess insulin sensitivity, patients will receive an intravenous infusion of insulin and – via a second intravenous access – increasing amounts of glucose to maintain euglycemia. Insertion of the necessary intravenous lines may cause the above-mentioned discomfort and a possible skin infection. Insulin infusion can induce hypoglycemia and hypokalemia. Either event is very unlikely, since patients undergo frequent blood glucose measurements and are constantly observed for the presence of hypoglycemic symptoms by an experienced nurse and/or physician. However, in order to prevent complications, two patent, well-functioning intravenous lines are required during this procedure. A stat potassium will be measured at the end of the insulin infusion, and oral KCL 40 mEq will be given if potassium is less than 3.5.

9. Magnetic Resonance Imaging (MRI) and Magnetic Resonance Spectroscopy (MRS): While MR scanning is thought to be safe, the procedure may cause anxiety in some patients since current equipment used at the Clinical Center uses a closed tube. Adult patients will be offered sedatives such as Valium if they express worry about being in a closed space. No intravenous contrast will be used in these studies. The hand-grip exercise may produce mild fatigue.
10. Lipoprotein lipase activity: The primary risk of lipase assays involving heparin infusion of 60 units/kg is bleeding (in <0.1% of subjects). Testing will not be performed in subjects at increased bleeding risk, including those with platelet counts, prothrombin time, and partial thromboplastin time outside the normal range within 48 hours of testing, those with history of recent peptic ulcer disease or gastrointestinal bleeding, or other bleeding diathesis. This test also involves minor risks associated with intravenous line placement.
11. Mixed meal: This test requires one IV, but no adverse effects are anticipated.
12. Carotid intima-media thickness: This is a non-invasive ultrasonographic test. No adverse effects are anticipated.
13. Hunger and pain questionnaires: Patients may find it a minor inconvenience to fill out the questionnaires, but no adverse effects are anticipated.
14. Liver biopsy: Risks and discomforts of liver biopsy are as follows:
 - a. Pain. About 20% of persons who undergo a liver biopsy experience pain in the side of body over the liver after the biopsy. This pain usually lasts from a few minutes to several hours and may require pain medication. In rare cases, the pain lasts a day or two.
 - b. Fainting. About 2% of persons pass out due to vasovagal reaction after a liver biopsy. This is unlikely to cause harm, as patients will be lying in bed during the biopsy. Atropine will be given to reverse the vasovagal reaction if it occurs, and may be given prior to the biopsy in individuals prone to these reactions.
 - c. Infection. A rare complication of liver biopsy is infection that spreads to the rest of the body because the needle goes through skin that is not completely clean or sterile or goes through infected bile (as occurs in patients with gallstones sometimes). Antibiotics can treat such infections.
 - d. Biopsy of another organ. In rare instances, the biopsy needle misses the liver and hits another internal organ, such as the lung, gallbladder, kidney, or intestine. This complication can be avoided by carefully selecting the site for the liver biopsy and using ultrasound to identify exactly where the liver is and the best position for the biopsy. Usually, the other organ is not damaged by the needle puncture; however, it is possible that surgery might be needed to repair the hole. The most important complication of liver biopsy is bleeding. A small amount of bleeding probably occurs in many patients after liver biopsy, but the amount of bleeding is usually too small to be detected or felt. Severe bleeding occurs in about one of every 1000 liver biopsies. Severe bleeding is most likely to occur in someone with cancer of the liver or with abnormal clotting studies, but bleeding can also occur in patients with mild forms of

- e. Risks and discomforts of medications used during liver biopsy are as follows: Three medications are often used during a liver biopsy: Xylocaine to numb the skin, a sedative such as Versed (midazolam) to make subjects drowsy during the biopsy, and atropine if subjects have a tendency to faint. All three medications are safe when given in the usual doses. In rare instances, they can induce allergic reactions which can be a skin rash, itching, wheezing, an asthma attack, or even anaphylaxis - or allergic shock. All of the allergic complications can and will be treated if they arise. Xylocaine, when given in high doses can also cause heart blockage, seizures, coma, or even death; but, in the doses given in this study it has no obvious effect on the heartbeat. Atropine can cause dryness of the eyes and mouth, difficulty focusing the eyesight, constipation and difficulty passing urine. All these side effects will disappear within a few hours. Versed or Midazolam for sedation causes sleepiness and forgetfulness. In high doses, it can cause over-sedation with coma and depression of breathing and even death. This medication is given in small amounts with careful monitoring of sedation. Standard medications and equipment used for conscious sedation will be available during the procedure.

7.10.3 Alternatives to participation

Participation in clinical trials is completely voluntary. Refusal to participate will not affect a subject's ability to participate in other studies at NIH or elsewhere.

7.11 Financial Compensation

All subjects will receive financial compensation for their time per Clinical Center guidelines for on-site visits, and additional compensation will be provided for specific procedures based on inconvenience units. See Appendix E. There will be no compensation for the additional 12 month extended open-label period.

7.12 Consent Procedures

Written consent will be obtained at the first inpatient visit from each subject after detailed explanations of the planned procedures by the principal or an associated investigator (as listed on face sheet). The consent process will take place prior to any study procedures, however, the research team will talk with the subjects prior to coming to NIH to determine eligibility and to provide dietary recommendations. The current NIDDK/NIAMS IRB-approved informed consent document will be signed by the subject and the Investigator. A witness will additionally sign the document to attest only to the validity of the signature of the subject, not the validity or quality of the consent. A copy of the consent will be given to the subject for future reference. The signed documents will be sent to the Medical Records Department for placement in the subject's permanent CC medical record. The consent process will additionally be documented in the electronic medical record (CRIS).

We do not plan or anticipate the enrollment of non-English speaking subjects. However, they are not excluded from participation either. If there is unexpected enrollment of a research participant for which there is no translated extant IRB-approved consent document, the Principal Investigator and/or those authorized to obtain informed consent will use the short form consent process as described in MAS Policy M77-2, NIH SOP 12, 45 CFR 46.117 (b), and 21 CFR 50.27 (b). The summary that will be used is the English version of the extant IRB-approved consent document. We request prospective IRB approval of the use of the short form consent process for up to a maximum of 5 requests (either for individual participants or families of participants) in a given language, and will notify the IRB at the time of continuing review of the frequency of the use of the short form. Should we reach the threshold of 5 subjects and/or families speaking a single language, we will request an additional use of the short form from the IRB and will notify the Board that we plan to have any consent documents frequently used with that population translated into the language(s) they speak.

Subjects have the right to withdraw participation from this protocol at any time.

7.13 Research Use, Storage and Disposition of Human Subjects' Samples and Data

For future reference and potential use, we will store all samples (blood or fluids) in our locked freezers for an unlimited period of time. Samples will be labeled with coded identifiers linked to patient identity only via a secured database. Research records and data with personal identifiers will be stored in our locked offices, the medical record department, and the electronic study database. The electronic study database will be maintained by Ionis Pharmaceuticals. Representatives of Ionis Pharmaceuticals will have access to research records and data with personal identifiers only when the representative is physically present in the NIH Medical Records department. The electronic study database will not contain any personal identifiers, although it will contain dates on which labs or tests are performed. This material will additionally be protected by medical record and computer access procedures. Access to records and data associated with personal information will be restricted to the Principal Investigator, Co-Investigators, study support staff, and NIH database support staff.

Stored samples and/or data may be sent to outside collaborating laboratories, or shared with other NIH collaborating investigators, to study questions related to lipodystrophy or its complications (including, for example: glucose metabolism, diabetes, obesity, weight, appetite, steatohepatitis, and lipid metabolism). Samples may be sent to outside commercial laboratories for analysis. Samples and data sent to outside laboratories and collaborators for analysis and/or testing will contain only coded numbers, without personal identifiers. Tech Transfer agreements will be completed before the exchange of samples and/or data with outside collaborators.

Subjects may request that unused samples be removed from our freezers and returned to the subject, or be destroyed. If no such request is made, we will keep samples until they are completely used or no longer of scientific value, at which time they will be destroyed. We do not plan to destroy personal medical information or stored data. The Principal Investigator will report loss or destruction of data or samples to the NIDDK/NIAMS IRB.

7.14 Collaborations

Metabolomic studies of plasma and liver biopsy specimens will be conducted in collaboration with [name] at University of Michigan. Deidentified samples will be shipped to the University of Michigan under a Material Transfer Agreement. Raw data from [name] will not be sent to us, but overall results will be shared.

Collaboration has been established with [name] [name] in Cambridge, England. Our direct physician contacts are [name] and [name]. The purpose of this collaboration is to share coded de-identified clinical data and results collected from subjects enrolled under this protocol at NIH. The Laboratory at Cambridge University will use the coded data and results, including laboratory, anthropometric, imaging and demographic data, to characterize the phenotype of patients affected by lipodystrophy and to study the association between phenotypes and causative genetic mutations, in order to better understand the pathogenesis and natural history of lipodystrophy, improve the diagnosis, and predict and assess response to treatment.

Collaboration has been established with [name] at the University of Texas Southwestern. This collaborator is a former associate principal investigator of our original leptin protocol, and is a world’s expert on syndromes of lipodystrophy. The purpose of this agreement is to transfer coded de-identified metabolic and clinical data, including laboratory, anthropometric, imaging and demographic data, to characterize the phenotype of patients affected by lipodystrophy and to study the association between phenotypes and causative genetic mutations, in order to better understand the pathogenesis and natural history of this disease, improve the diagnosis, and predict and assess response to treatment.

Collaboration has been established with [name], a board-certified pediatric endocrinologist and Professor of Pediatrics and Medicine at Baylor College of Medicine. Our direct site contact will be [name]. The purpose of the collaboration is to assist in the conduct of the clinical studies determining the rates of glucose production and gluconeogenesis in subjects with a variety of forms and severity of lipodystrophy. This will include the analysis of coded human subject samples and interpretation of the results.

Collaboration has been established with [name]. and [name]. are professors at the University of Colorado Anschutz Medical Campus. The secondary study objective of this protocol was to explore the mechanism of action of apoC-III ASO by measuring the lipoprotein lipase (LPL) activity and lipoprotein particle distribution to evaluate if we can strengthen the connection between LPL activity and the metabolic disturbances which is an area that has not been researched. Therefore, the pre- and 10 minutes post-heparin infusion samples collected on the 5 enrolled partial lipodystrophy patients who were treated with ApoC3 antisense oligonucleotide will be shared with the collaborators who will run LPL assays. Samples will be coded and the collaborators will share the results of their analysis.

Collaboration has been established with [name]. and [name], professor of Gunma University Graduate School of Medicine (Department of Clinical Laboratory Medicine) located in Maebashi, Gunma, Japan. The collaborators are interested in determining 4 types of markers found in the plasma of patients with lipodystrophy. These markers (or “assay systems”) were developed in [name] laboratory and include: (1) LPL activity (post-heparin plasma) and mass, (2) HTGL activity (post-heparin plasma) and mass, (3) GPIHBP1 mass, and (4) GPIHBP1 autoantibody. They will run the above stated assays using specimens collected before and after leptin treatment. Research has shown that Leptin lowers triglycerides in these patients, and hence we would hypothesize that LPL and HTGL activity might be increased after leptin treatment. Therefore, we will send to the collaborators deidentified plasma collected from the lipodystrophy patients to test this hypothesis.

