4.1 Design/Randomization

This study has two components. Initially, subjects will receive ISIS 304801 or placebo, in a 1:1 randomized, double-blinded fashion for 16 weeks. Randomization will occur after verification that all eligibility criteria have been met. The randomization will be stratified by use of lipid-lowering medications. After completion of 16 weeks, all subjects will receive ISIS 304801 for 12 months in an open-label extension (OLE) phase. After discontinuation of ISIS 304801 (due to study end or any other reason) subjects will be followed for an additional 12 week withdrawal phase when possible. Patients who experience benefit (triglyceride lowering $\geq 50\%$) may receive an additional 12 months of open label drug (up to 24 months, total). This period may initiate immediately following the standard 12 month OLE, or following the withdrawal phase.

- 1° outcome (Δ in log₁₀ triglycerides):
 - C vs D
 - F vs G
- 2°/3° outcomes – within subject comparisons:
 - C vs E
 - F vs H
- Placebo vs drug comparisons
 - C vs H

1

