5.1 Sample Size Justification

The primary outcome variable is the change in log₁₀ fasting triglycerides from before treatment to 16 weeks of active drug treatment compared to placebo groups.

Preliminary data are available for 28 patients treated with ISIS 304801 and 24 treated with placebo. For the ISIS 304801 group, these data show a difference from baseline to follow-up of -423 (SD 400, 95% CI -578 to -268) mg/dL and -0.485 (SD 0.221, 95% CI -0.57 to -0.40) log₁₀ mg/dL. Converting the difference in log₁₀ mg/dL to a percent change [$100 \times (10^{-0.485} - 1)$] results in a percent change of -67% (95% CI -73% to -60%). For the placebo group, the absolute change is -12 (SD 406, 95% CI -12 to 184) mg/dL and -0.011 (SD 0.224, 95% CI -0.105 to 0.084) log₁₀ mg/dL. The percent change for the placebo group is -3% (95% CI -21% to 21%).

For comparison of placebo and ISIS 304801 we have chosen a SD of 0.25 log₁₀ mg/dL and a difference of 0.50 log₁₀ mg/dL. A trial with 5 patients in each group has 79% power to detect a difference of 0.50 log₁₀ mg/dL triglycerides in the change from baseline to follow-up between the ISIS and placebo groups, assuming a SD of 0.25 log₁₀ mg/dL and a two-sided significance level of 0.05.

Where preliminary data were available, sample size calculations were performed for secondary and tertiary study outcomes in addition to the primary outcome. The preliminary data and power estimates for a sample size of 10 subjects (using one-sample t-test for off versus on drug comparisons) are summarized in the table below. Based on these calculations, the study should be adequately powered to detect differences in total body insulin sensitivity, hepatic insulin sensitivity, fasting glucose, apoC-III serum level, HDL-C, VLDL-C, and apolipoprotein B48.

Based on these calculations, we plan to enroll a maximum of 20 patients, with a goal of 10 patients completing the study (defined as completing 16 weeks of active drug treatment). The accrual ceiling of 20 is planned because subjects will consent to the study prior to screening, thus we are accounting for up to 10 screen failures in the accrual ceiling.

	Outcome	Model	Treatment	Treat- ment Duration	Mean of Δ on-off drug (SD)	Power
Primary outcome	Absolute change log[serum triglycerides] (mg/dL)	High TG +/- diabetes and/or fibrate	ApoCIII ASO 300 mg/wk	16 wk	-0.48 (0.22)	>0.95
	% change serum triglycerides (%)	High TG +/- diabetes and/or fibrate	ApoCIII ASO 300 mg/wk	16 wk	-63 (20)	>0.95

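### The 79% power in 5.1 is right for 5 v 5 evaluable at Week 16, but the plan does not secure that number, and the count of five in 7.14 must be reconciled with it

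*Combined protocol and SAP*

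**What the plan says.** Section 4.1 sets a 1:1 allocation: "subjects will receive ISIS 304801 or placebo, in a 1:1 randomized, double-blinded fashion for 16 weeks". It is stratified by lipid-lowering medication, and all subjects then receive active drug in the open-label extension.

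Section 5.1 powers the primary comparison: "A trial with 5 patients in each group has 79% power to detect a difference of 0.50 log₁₀ mg/dL triglycerides", "assuming a SD of 0.25 log₁₀ mg/dL and a two-sided significance level of 0.05". It sets a maximum of 20 enrolled and a goal of 10 completers, where completing is "defined as completing 16 weeks of active drug treatment". The gap between 20 and 10 is explained by consent preceding screening: "thus we are accounting for up to 10 screen failures in the accrual ceiling". No dropout rate is given.

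Section 5.2 compares the arms on change from baseline at Week 16, by two-sample t-test or Wilcoxon rank-sum test as appropriate. It uses all available data regardless of adherence and takes p of 0.05 or less as significant. Section 6.2.2.5 adds that a subject missing more than two doses before Week 13 may not be evaluable for the primary endpoint.

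Section 7.14, describing samples to be sent to a collaborating laboratory, refers to "post-heparin infusion samples collected on the 5 enrolled partial lipodystrophy patients who were treated with ApoC3 antisense oligonucleotide".

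**The concern.** With five per arm, the design has no slack: one missing Week 16 value takes power below the stated figure. The protocol itself makes losses foreseeable, through its withdrawal criteria and its evaluability caveat in 6.2.2.5. Yet 5.1 budgets for screen failures alone and fixes no number per arm.

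The sentence in 7.14 raises a larger doubt. It is in the past tense and uses a definite article. Because placebo-first patients also go on to active drug, having been treated does not single out one arm. Its most natural reading is that five patients had been enrolled in all when it was written. If that was the final number, a non-significant result would be read against 79% when the chance of success at the planning effect was about one in three.

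**Working it through.** **Inputs, from 5.1.** Difference 0.50 log10 mg/dL, SD 0.25, two-sided alpha 0.05, so the standardised difference is 0.50/0.25 = 2. The test is the two-sample t-test of 5.2.

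**Formula.** With n1 and n2 evaluable, df = n1 + n2 − 2 and the noncentrality parameter is ncp = 2/√(1/n1 + 1/n2). Power is the probability that a noncentral t on df, with that ncp, falls beyond ±t(0.975, df).

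**The plan's own figure.** At 5 v 5, df = 8, critical t = 2.306 and ncp = 2/√0.4 = 3.162. Power is 79.05%, so the stated 79% is reproduced.

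**Other numbers, same inputs.** The 95% CI half-width is t × 0.25 × √(1/n1 + 1/n2). The smallest possible two-sided exact rank-sum p, without ties, is 2/C(n1+n2, n1).

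| Evaluable at Week 16 | Critical t | ncp | Power | CI half-width (log10) | Smallest rank-sum p |
|---|---|---|---|---|---|
| 5 v 5 | 2.306 | 3.162 | 79% | 0.36 | 2/252 = 0.008 |
| 6 v 4 | 2.306 | 3.098 | 77% | 0.37 | 2/210 = 0.010 |
| 7 v 3 | 2.306 | 2.898 | 72% | 0.40 | 2/120 = 0.017 |
| 5 v 4 | 2.365 | 2.981 | 73% | 0.40 | 2/126 = 0.016 |
| 4 v 4 | 2.447 | 2.828 | 66% | 0.43 | 2/70 = 0.029 |
| 5 v 3 | 2.447 | 2.739 | 63% | 0.45 | 2/56 = 0.036 |
| 4 v 3 | 2.571 | 2.619 | 56% | 0.49 | 2/35 = 0.057 |
| 3 v 2 | 3.182 | 2.191 | 33% | 0.73 | 2/10 = 0.20 |
| 4 v 1 | 3.182 | 1.789 | 24% | 0.89 | 2/5 = 0.40 |

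Two things follow. At 3 v 2 the interval half-width (0.73) exceeds the effect sought (0.50). And with seven or fewer evaluable patients the rank-sum test cannot reach 0.05 whatever the data, because 4 v 3 is the most favourable split of seven and its smallest p is 0.057.

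**Dropout.** The documents give no rate, so a range is assumed. Suppose 10 are randomised 5:5, each is lost independently and none is replaced. Average power is then 75.6% at 5% dropout, 71.8% at 10%, 67.7% at 15%, 63.2% at 20% and 53.4% at 30%. The number to randomise for 10 evaluable is 10/(1 − d), rounded up: 12 at 10%, 13 at 20%, 15 at 30%. All are within the ceiling of 20 if enough screening places remain unused.

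**Readings of the five in 7.14.**
- Total enrolment: 3 v 2 or 4 v 1, so 33% or 24%.
- The arm randomised to active drug, beside five on placebo: 79%, unchanged.
- Enrolment to date: final power depends on later accrual.
- Patients with usable heparin samples: says nothing about the total. The risks section withholds this test from subjects at increased bleeding risk, so such a subset could exist.

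**The case against.** **The 79% is a correct planning figure.** This stands. Nothing in 5.1 contradicts it, and the point concerns sample size and power, not arithmetic.

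**A reader might infer from 7.14 that the trial closed with five patients, so its power is 33%.** The documents do not support that as fact. The sentence is about sample sharing. It is undated and gives neither the arm nor the number with Week 16 data, and the other three readings cannot be excluded. What stands is that the wording fits total enrolment best and needs clarifying.

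**A reader might infer that the completer definition undercounts Week 16 data.** It does not. An active-first patient meets it on reaching Week 16, and a placebo-first patient must pass Week 16 before starting active drug. Ten completers therefore imply at least ten patients who reached Week 16. A placebo-first patient lost after Week 16 still contributes to the primary analysis. The remaining gap is narrower: nothing requires five per arm or an actual Week 16 measurement.

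**A reader might infer that dropout cannot be absorbed.** That is also too strong. The allowance is for up to ten screen failures, prescreening is meant to keep failures low, and no text forbids using spare places to replace losses. Dropout is unplanned, and the no-replacement figures are a worst case.

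**The planning inputs are slightly cautious.** The preliminary data in 5.1 give a difference of 0.485 − 0.011 = 0.474 and a pooled SD of √[(27 × 0.221² + 23 × 0.224²)/50] = 0.222. Power is then 84% at 5 v 5, 78% at 5 v 4 and 71% at 4 v 4. This softens the loss figures but does not rescue 3 v 2 (37%).

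**Enrolled numbers belong in the results report, not the design section.** This is partly fair. But once an amended protocol mentions an enrolment count that may be half the design number, leaving 79% beside it without comment is misleading.

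**Conclusion.** The point holds as a gap in the sample-size plan and an unreconciled statement. The 79% is right for 5 v 5 evaluable at Week 16, but neither the accrual rule nor the completer target secures that number. One loss costs about 6 or 7 percentage points (73%), and two losses about 13 to 16 (66% or 63%). These figures assume the planning difference and SD, the t-test, ten randomised 5:5 and no replacement.

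The 33% (3 v 2) and 24% (4 v 1) apply only if the five in 7.14 is final total enrolment, which the documents leave open. The accrual and target gap stands on any reading of 7.14.

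**What to change.** In 5.1:
- Define the accrual target as five patients per arm with a measured blinded-phase Week 16 triglyceride, and keep the active-drug completer count as a separate goal for the within-subject outcomes.
- Say that screening places left unused under the ceiling of 20 may replace losses, and state an assumed dropout rate.
- State that 79% holds only with no losses, and give 73% at 5 v 4, 66% at 4 v 4 and 63% at 5 v 3.

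Reconcile 5.1 with 7.14 by stating what the five refers to, with enrolment by arm. If enrolment closed at five in total, replace 79% with about 33% for 3 v 2 (24% for 4 v 1).

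In 5.2, make the t-based difference in log10 change with its 95% CI the primary result. Rule out the rank-sum test wherever its smallest possible p exceeds 0.05, which includes every split of seven or fewer. Reconcile the use of all available data with the evaluability caveat in 6.2.2.5, since the choice changes the evaluable number.

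The cost is a few sentences in 5.1, 5.2, 6.2.2.5 and 7.14. The ceiling of 20 and the conduct of visits are unchanged.
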